**Figure 1 - Raymond Classification of Angiographic Results**

When assessing effectiveness, all images will be reviewed by an independent Core Lab per a Core Lab Radiographic Imaging Protocol. The Core Lab will be selected and qualified by the Sponsor prior to enrollment of the first study subject, and will develop the Core Lab Radiographic Imaging Protocol prospectively. To avoid interobserver variability, the Sponsor will use a Core Lab where all Core Lab readings will be performed by a single reviewer who will be blinded to assessments made by the clinical sites. In order to ensure reliable collection of images suitable for analysis, the Core Lab that is selected will develop guidelines for image acquisition, and will share these guidelines with clinical sites participating in the study.

#### **2.4.1.2 Primary Safety Endpoint**

The primary safety endpoint is:

Any major ipsilateral stroke or neurological death within 12 months.

An ipsilateral stroke will be defined as an acute episode of focal or global neurological dysfunction due to brain or retinal infarction, or due to an intracranial hemorrhage inclusive of subarachnoid, intraventricular or intraparenchymal hemorrhage, occurring in the same hemisphere as the target aneurysm.

A major ipsilateral stroke will be defined as an ipsilateral stroke that is associated with an increase of 4 or more points on the NIHSS at 24 hours after symptoms onset.

Note: For the purpose of consistency with the primary endpoint definition, strokes in the posterior circulation adjudicated as being strokes “within the treated vascular territory” will be called “ipsilateral” strokes.

### **2.4.2 Secondary Endpoints**

#### **2.4.2.1 Effectiveness**

The secondary effectiveness endpoints identified below will be assessed post-index procedure through 12 months per the schedule requirements.

# **Safety and Effectiveness of the Treatment of Wide Neck, Saccular Intracranial Aneurysms with the Neuroform Atlas™ Stent System**

## **Short Study Name: ATLAS**

- Procedural technical success (defined as the proportion of subjects in whom the stent was successfully delivered to, and deployed at, the target location)
- Incidence of retreatment
- Incidence of recanalization (defined as a categorical increase in aneurysm filling over time after some degree of occlusion has been achieved initially)
- Incidence of parent artery stenosis at the target aneurysm location (>50% stenosis)
- Incidence of stent migration based on follow up angiogram
- Proportion of aneurysms with occlusion of Raymond Class 1, 2 or 3
- Proportion of aneurysms with occlusion of Raymond Class 1 and 2 combined
- Incidence of progressive occlusion at the target aneurysm location

### **2.4.2.2 Safety**

The secondary safety endpoint is the percent of subjects experiencing one or more serious adverse events (SAE) through 12 months post-index procedure within the following categories (definitions are provided in the Appendices).

- New or worsening major ipsilateral stroke as measured by NIHSS
- Device related serious adverse events
- Subarachnoid hemorrhage (SAH)
- Aneurysm rupture

### **2.5 Study Success/Failure Criteria**

- For both the anterior and posterior circulation cohorts, the lower limit of the 95% confidence interval of the proportion of subjects who achieve the primary effectiveness endpoint (i.e., complete aneurysm occlusion, in the absence of retreatment and > 50% parent artery stenosis at the target location, based on angiographic assessment at 12 months) is >50%.
- For the anterior circulation cohort, the upper limit of the 95% confidence interval of the proportion of subjects who experience the primary safety endpoint (i.e., any major ipsilateral stroke or neurological death within 12 months) is <20%.
- For the posterior circulation cohort, the upper limit of the 95% confidence interval of the proportion of subjects who experience the primary safety endpoint (i.e., any major ipsilateral stroke or neurological death within 12 months) is <25%.

### **2.6 Study Population and Source of Subjects**

Subjects over 18 years of age presenting with wide neck, intracranial, saccular aneurysms requiring treatment with stent-assisted coiling may be eligible for study participation. Potential study candidates or their legal representatives will provide informed consent prior to any data collection. A screening and enrollment log will be provided to study sites to maintain a record of all screened subjects.

Subjects will be identified and recruited by Clinical Investigators and/or their designated research staff at a maximum of up to 40 investigative sites. Clinical investigators selected to participate in the study may enroll and treat a maximum of 20% of subjects enrolled in either cohort.

Subjects who sign an IRB or EC approved consent form will be considered enrolled in the study. Any subject consented, whether treated or not, will be assigned a screening number. Subjects who consent to participate but withdraw or are found to be ineligible prior to initiation of the procedure will be considered a screening failure, and the reasons for the screening failure will be documented on the site

[figure not shown]
# **Safety and Effectiveness of the Treatment of Wide Neck, Saccular Intracranial Aneurysms with the Neuroform Atlas™ Stent System**

## **Short Study Name: ATLAS**

screening log. In all cases where subjects are consented but not treated using a Neuroform Atlas™ Stent, replacement subjects will be enrolled. Subjects in whom an investigational procedure is attempted but stent delivery is unsuccessful will be followed through the two month follow-up visit; these subjects will be considered treatment failures but will not be evaluated for the primary endpoints at 12 months. All treated subjects with successful stent delivery and deployment will be evaluated for the primary endpoints at 12 months post-procedure.

For long-term follow-up, subjects will be asked to return for clinical follow-up visits at 2 years and 3 years ( $\pm$  6 months) post-index procedure.

The study flow is depicted in **Figure 2**.

**Figure 2 - Schematic of Study Flow**

### **2.6.1 Inclusion Criteria**

Candidates must meet ALL of the following inclusion criteria:

1. Subject is between 18 and 80 years of age
2. Subject has a documented, wide neck (neck  $\geq$ 4mm or a dome-to-neck ratio  $<$ 2), intracranial, saccular aneurysm arising from a parent vessel with a diameter of  $\geq$  2mm and  $\leq$  4.5 mm, which will be treated with bare metal coils
3. Subject or legal representative is willing and able to provide informed consent

## **Safety and Effectiveness of the Treatment of Wide Neck, Saccular Intracranial Aneurysms with the Neuroform Atlas™ Stent System**

### **Short Study Name: ATLAS**

4. Subject is willing and able to comply with protocol follow up requirements

#### **2.6.2 Exclusion Criteria**

Candidates will be excluded from this study if they do not meet the specific inclusion criteria, or if ANY of the following exclusion criteria are present:

1. Subject has known multiple untreated cerebral aneurysms, other than non-target blister aneurysm, infundibulum, or aneurysm measuring <3mm for each of three dimensions assessed (height, width, and depth) that will not require treatment during the study period
2. Subject has a target lesion that is a blister aneurysm, infundibulum, or aneurysm measuring <3mm for each of three dimensions assessed (height, width, and depth)
3. Subject has a target aneurysm that will require an Investigator to intentionally leave a neck remnant in order to preserve blood flow in a bifurcation or branch
4. Subject has undergone coiling or stenting of a non-target intracranial aneurysm within 30 days prior to study treatment
5. Subject has a target aneurysm in the anterior circulation proximal to the superior hypophyseal ICA
6. Subject has acute target aneurysm rupture less than 14 days prior to study treatment
7. Subject has a Hunt and Hess score  $\geq 3$  or a premorbid mRS score  $\geq 4$
8. Subject has an admission platelet count of  $<50,000$ , any known coagulopathy, or an International Normalized Ratio (INR)  $>3.0$  without oral anticoagulation therapy
9. Subject has a known absolute contraindication to angiography
10. Subject has evidence of active cancer, terminal illness, or any condition which, in the opinion of the treating physician, would/could prevent the subject from completing the study (e.g., a high risk of embolic stroke, atrial fibrillation, co-morbidities, psychiatric disorders, substance abuse, major surgery  $\leq 30$  days pre-procedure, etc.)
11. Subject has a known absolute contraindication to the use of required study medications or agents (e.g., heparin, aspirin, clopidogrel, and radiographic contrast agents etc.)
12. Subject is female and is pregnant or intends to become pregnant during the study
13. Subject has Moya-Moya disease, arteriovenous malformation(s), arteriovenous fistula(e), intracranial tumor(s), or intracranial hematoma(s) (unrelated to target aneurysm)
14. Subject has significant atherosclerotic stenosis, significant vessel tortuosity, vasospasm refractory to medication, unfavorable aneurysm morphology or vessel anatomy, or some other condition(s) that, in the opinion of the treating physician, would/could prevent or interfere with access to the target aneurysm and/or successful deployment of the Neuroform Atlas™ Stent
15. Subject has had previous treatment (e.g., surgery, stenting) in the parent artery that, in the opinion of the treating physician, would/could prevent or interfere with successful use of the Neuroform Atlas™ Stent System and/or successful deployment of embolic coils
16. Subject has undergone previous stent-assisted coiling of the target aneurysm

#### **2.6.3 Withdrawal and Replacement of Subjects**

While study withdrawal is discouraged, subjects may withdraw from the study at any time, with or without reason and without prejudice to further treatment. Withdrawn subjects who received treatment will not undergo any additional follow-up, nor will they be replaced (the justified sample size considers an estimated allowance for attrition). If a subject is consented and not treated, a replacement subject will be enrolled.

#### **2.7 Method of Assigning Subjects to Treatment**

This is a prospective single arm study in which all subjects who present for stent-assisted coiling, provide informed consent, and meet inclusion/exclusion criteria may receive treatment (Neuroform Atlas™ Stent System). Eligible subjects will be consecutively enrolled at each site. Reason for screen failures will be documented.

# **SAfety and Effectiveness of the Treatment of Wide Neck, Saccular Intracranial Aneurysms with the Neuroform Atlas™ Stent System**

## **Short Study Name: ATLAS**

### **2.8 Measures to Increase Validity and Minimize Bias**

The following measures will be in place to increase validity and minimize bias.

1. Multiple clinical trial sites will be utilized to ensure generalizability of results and minimize site/operator effect.
2. The primary study effectiveness endpoint will be based on angiographic readings from an independent Core Lab blinded to operator assessment of outcomes and clinical data. Pre-determined evaluation criteria will be applied to review and analysis of the data.
3. The primary safety endpoint will be based on the incidence of established safety parameters as adjudicated by an independent CEC.
4. Study monitors will review and verify data collection forms against source documentation to ensure that there are no missing, illegible or incorrect data. Missing, illegible or incorrect data will be corrected following ICH/GCP guidelines.
5. Investigative site personnel will contact subjects prior to their scheduled study visits to increase compliance with the subject follow up protocol.

## **3 Study Procedures**

### **3.1 Subject Screening**

Subjects will not be recruited until the Food and Drug Administration (FDA), local regulatory authorities (as applicable), and the local Institutional Review Board (IRB) or Independent Ethics Committee (IEC) have approved the study. Site Investigators will assess potential subjects with wide neck intracranial aneurysms for enrollment in the study. The subject's suitability for treatment with the Neuroform Atlas™ Stent System will be evaluated based on medical and anatomical criteria as outlined in the inclusion/exclusion criteria. Angiograms (CTA, DSA or MRA) to determine suitable subjects may be generated up to 6 months prior to the treatment date.

*NOTE: Data obtained prior to consenting as standard of care can be used for screening and completion of study CRFs.*

If a subject meets the eligibility criteria for the study, this will be documented in the site's study screening log. If a subject fails to meet the eligibility criteria, the reason(s) for this will likewise be documented in the screening log. The screening log serves as a method for the Sponsor to ensure that there is no selection bias in the trial.

### **3.2 Informed Consent**

Subjects will be informed by the Investigator or the Investigator's designee that they are free to refuse participation in this research study. If they elect to participate, it will be made clear that they may withdraw from the study at any time without prejudicing further care.

The Investigator or the Investigator's designee will inform subjects that their medical records will be subject to review by the Sponsor or appropriate regulatory bodies. This information will be used during the analysis of the results of the clinical study, but the subjects' identities will be treated as confidential. Subjects will be assigned a unique identification code. This code will be used on all data and data collection forms during the study period. It will not reveal the subject's identity.

The Investigator will explain the conditions of the study, giving the subject sufficient time to ask questions and to consider whether or not they want to participate. Subjects will be informed that active study participation is expected through their 12-month follow-up visit, but the informed consent form will allow for continued follow-up through 60 months post-treatment should longer term follow-up

## **SAfety and Effectiveness of the Treatment of Wide Neck, Saccular Intracranial Aneurysms with the Neuroform Atlas™ Stent System**

### **Short Study Name: ATLAS**

become necessary. Eligible subjects who agree to participate will be asked to sign and date an IRB approved informed consent form. One copy of the signed and dated informed consent form shall be returned to the Investigator and filed in the subject's case history, and one copy shall be provided to the subject for his/her personal records.

#### **3.3 Subject Withdrawal**

A subject has the right to voluntarily withdraw from the study at any time and for any reason without prejudice to his or her future medical care by the Investigator(s) or the Institution. The Investigator(s) may elect at any time to withdraw a subject from the study for any reason unrelated to the study treatment if such a decision is in the subject's best medical interest. If a subject discontinues the study after undergoing the investigational procedure, or is withdrawn by the Investigator(s), as much follow-up data as possible will be obtained. Attempts will be made to retrieve follow-up data, prior to the time point at which voluntary consent was withdrawn, in particular regarding possible AEs at the time of study discontinuation.

An enrolled subject who is found to be ineligible to participate in the study after signing the consent form will be exited from the study at determination of ineligibility. If a subject is consented and not treated, a replacement subject will be enrolled. If a subject is withdrawn from the study after treatment for any reason, he or she will not be replaced.

All enrolled subjects are expected to continue to participate in the study through the final follow up assessment as outlined in this protocol, or until such time as the Sponsor or the Sponsor's authorized designee notifies the Investigator in writing that further follow up is no longer required, except in the event of death, or upon the subject's written request for early withdrawal from the clinical study. If a request for early withdrawal is received, a copy of the request should be forwarded directly to the Sponsor or the Sponsor's authorized designee for documentation purposes.

#### **3.4 Lost to Follow Up**

A subject will be considered "lost to follow up" and will be terminated from the study when he or she can no longer be reached by study staff and have missed study visits. The site must notify the Sponsor of subject status, and must consult with the Sponsor regarding discontinuation of any study subject prior to ceasing all attempts to contact such subjects. A subject may only be categorized as lost to follow up if the following criteria are met:

- Failure to complete 12-month or two consecutive follow up visits, and
- Documentation of three unsuccessful attempts by the Investigator or his/her designee to contact the subject and/or next of kin

For long-term follow-up, subjects will be considered lost-to-follow-up if the documentation criterion is met.

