### **3.10 Follow Up Visits**

Enrolled and treated subjects will return for follow-up visits and collection of primary and/or secondary endpoint data as required at two, six, and twelve months. Long-term outcomes data will be collected at

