### **Twelve Months (365d) ± 2 Months Post-Implant:**

- Neurological examination (including global neurological assessments and evaluation for cranial nerve deficits)
- Neurologic rating/grading scales including the following:
  - mRS (all subjects)
  - NIHSS (all subjects)
  - Hunt and Hess (for subjects who previously had a ruptured aneurysm and evidence of subarachnoid hemorrhage)
- Angiography (DSA)

*NOTE: 12-month angiography (DSA) is used to assess the primary endpoint and is required for all subjects*

- Assessment and documentation of any adverse events arising since the previous follow-up visit
- Assessment of compliance to the antiplatelet regimen
- Quality of Life assessment

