### **4.3 Eligibility of Subjects, Exclusions and Missing Data**

All efforts will be made to avoid any missing data, especially data related to the primary endpoints. Subjects who suffer neurological death prior to one year follow up will be imputed as Raymond 3 (the worst case) in the analysis of the primary effectiveness endpoint. Regression methods will be used to impute missing endpoint data. For either the safety endpoint or the effectiveness endpoint, five separate imputed data sets will be constructed in this manner. Inferences will then be completed using pooled estimates across the five data sets. In the event that no predictor variables can be found for the regression models, missing data will be imputed by a random draw from observed data for patients with similar baseline characteristics (e.g., gender, aneurysm location, race, etc.) as those with the missing data.

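### Section 3.4 lets an unreachable subject who missed the 2- and 6-month visits be closed out from about month 7, before the 12-month angiogram is due, with no required retry

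*Combined protocol and SAP*

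**What the plan says.** Section 3.4 states the consequence first: a lost subject "will be terminated from the study when he or she can no longer be reached by study staff and have missed study visits". The label may be used only when two criteria are both met. One concerns visits: "Failure to complete 12-month or two consecutive follow up visits, and". The other concerns contact: "Documentation of three unsuccessful attempts by the Investigator or his/her designee to contact the subject and/or next of kin". In addition, the site "must consult with the Sponsor regarding discontinuation of any study subject prior to ceasing all attempts to contact such subjects".

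Section 3.10 schedules follow-up visits "as required at two, six, and twelve months". Its note on the 12-month visit says that "12-month angiography (DSA) is used to assess the primary endpoint and is required for all subjects". The primary safety endpoint (Section 2.4.1.2) counts major ipsilateral stroke and neurological death over the same 12 months.

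For the post-approval study (PAS), Section 3.4 drops the visit criterion: "For long-term follow-up, subjects will be considered lost-to-follow-up if the documentation criterion is met".

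Section 4.3 opens with the aim that "All efforts will be made to avoid any missing data, especially data related to the primary endpoints", and then provides for imputation of whatever endpoint data are missing.

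**The concern.** The effectiveness endpoint is read from one examination, the 12-month angiogram. The 2- and 6-month visits collect mRS, adverse events and antiplatelet compliance, with NIHSS and imaging only under certain conditions. A subject can miss both and still supply the effectiveness outcome. A rule that permits closure on the strength of those two visits can therefore end follow-up before the endpoint is measurable, and can cut short the safety period.

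More is at stake than a few evaluable subjects. People who cannot be reached between months 2 and 7 need not resemble those who can, and Section 4.9 itself acknowledges that adverse events can keep patients from taking part and so make censoring informative. The outcomes of lost subjects are imputed from regression models or from similar observed subjects. The worst-case rule in Section 4.3, which scores a neurological death as Raymond 3, works only if the death is known.

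**Working it through.** **1. The plan's own attrition figure.** Section 4.2 enrols 180 per cohort to yield 153 evaluable at 12 months with 15% attrition. 180 × (1 − 0.15) = 153, so the figure reproduces. The allowance is 180 − 153 = 27 subjects per cohort, for all causes of loss.

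**2. What the consecutive-visit arm does.** The visits through 12 months are at 2, 6 and 12 months. The consecutive pairs are (2, 6) and (6, 12). The second pair is already covered by the arm on the 12-month visit. In this phase, then, the only thing the consecutive-visit arm adds is to let the visit criterion be met before the 12-month visit is due.

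**3. Timing.** Inputs from Table 2 and Section 3.10: 6-month visit at 180 days ± 1 month; 12-month visit at 365 days ± 2 months. Assumptions: a visit counts as missed when its window closes, and 1 month = 30 days.

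- The 6-month window closes on day 180 + 30 = 210 (month 7).
- The 12-month window opens on day 365 − 60 = 305 (month 10) and closes on day 365 + 60 = 425 (month 14).
- From possible closure to opening: 305 − 210 = 95 days, about 3 months.
- From possible closure to the end of the window: 425 − 210 = 215 days, about 7 months.

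With 31-day months the two gaps are 92 and 216 days, so the result does not depend on the convention.

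**4. What brings such a subject back.** The relevant texts, side by side:

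- Section 3.4 sets no spacing or timing for the three attempts, no retry once the 12-month window opens, and no stroke or vital-status check.
- Section 3.3 gives a general instruction to collect what follow-up data can be had after discontinuation. It names neither the 12-month angiogram nor its window. It also expects subjects to continue to the final assessment unless they die, ask in writing to leave, or the sponsor gives written notice; being unreachable is not on that list.
- Section 2.8 has sites contact subjects ahead of scheduled visits, but does not say that this applies to a subject already terminated.
- Section 4.9 treats subjects lost to follow-up as no longer available to the PAS, whereas the PAS mITT definition in Section 4.4 removes only those who withdrew, died or refused.
- Section 3.2 says that the consent form allows follow-up to 60 months, so a later attempt on a subject who has not withdrawn is foreseen.

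**5. Size, by assumption only.** The documents give no rate for this pattern. If 2% to 5% of a cohort were closed this way, that would be 0.02 × 180 = 3.6 to 0.05 × 180 = 9 subjects, or 3.6/27 = 13% to 9/27 = 33% of the allowance. Taking 9 more losses beyond the plan, complete cases only, the exact 95% interval rule and a true rate of 62%:

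| Evaluable | Successes needed for lower limit > 50% | Power |
|---|---|---|
| 153 | 90 | 81.4% |
| 153 − 9 = 144 | 85 | 79.5% |

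(The plan's 85% at n = 153 matches a normal approximation, 85.1%; the exact rule gives 81.4%. That is a separate matter.) The planned analysis imputes missing values, so these are not its power. They show only that lost numbers would matter little here; any harm would come mainly from non-random loss, which cannot be sized from the documents.

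**The case against.** A reader might infer that missing the two early visits is enough to end participation. The text does not support that. The two criteria are joint, the subject must be unreachable, next of kin may be among those tried, the sponsor must be consulted before contact attempts cease, and the wording sets minimum conditions rather than an automatic trigger.

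A reader might also infer that the lost angiograms and strokes are recoverable. That is not shown either. Anyone so classified was out of reach at the time, no re-contact rate is given, and the number who could be reached later may be near zero. Events already recorded stay in the data.

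Other provisions soften the effect: the general retrieval instruction in Section 3.3, multiple imputation in Section 4.3, a descriptive account of lost subjects in Section 4.8, and a 15% allowance for attrition of any kind. For the PAS, the analyses are descriptive, adverse events may be gathered by chart review or telephone (notes to Table 2), and Section 4.9 plans sensitivity analyses on loss patterns. Finally, anterior-circulation approval in May 2019 precedes this revision, so rewording can hardly alter that cohort's 12-month data.

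All of this stands, and it limits the claim. It leaves one gap: none of these provisions keeps the record open until month 14, requires a retry when the angiogram is due, or requires stroke and vital status to be established.

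**Conclusion.** The point holds as a gap in a stated rule. Section 3.4 permits termination from about month 7, roughly 3 months before the 12-month angiogram can be done and 7 months before its window closes, for a subject who missed the 2- and 6-month visits and could not be reached in three attempts. The timing rests on the stated windows and on counting a visit as missed when its window closes.

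The number affected, the number later reachable and the direction of any bias are unknown; the 2% to 5% range is an assumption, not evidence. The benefit for the 12-month endpoints is confined to subjects not yet past month 14, and the documents do not say how many remain. The PAS rule is a secondary matter and touches descriptive analyses only. A change is still worth making, because it is inexpensive and serves the plan's own aim of avoiding missing primary endpoint data.

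**What to change.** In Section 3.4:

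- Do not classify a subject as lost for the 12-month endpoints until the 12-month window has closed (month 14) without a visit.
- Keep subjects who missed the 2- and 6-month visits in the study, and retry contact with both the subject and next of kin within months 10 to 14.
- Where consent allows, seek stroke and vital status through 12 months from records for anyone still not reached.
- As a secondary change, do not classify a subject as lost in the PAS until the last visit window that applies to that subject has closed.

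The cost is protocol wording and a few more contact attempts. The drawback is that records stay open longer, so final subject accountability is settled later.
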